Note: Study medication will be provided in blister packs that are prepared by the PENN Investigational Drug Service and shipped to all three study sites. For the University of Pennsylvania, each blister pack will have a patient randomization number and the dosing schedule for each time on each inpatient study day, as summarized in the Study Schematics 4.0 below. For the two external sites, patient randomization will be generated by the site pharmacy or designated unblinded person, who receives the blister packs from the PENN Investigational Drug Service with the dosing schedule for each day.

The doses for each time of each day will be in separate compartments. Lofexidine will be 0.18 mg pink tables; pregabalin or pregabalin placebo will be in capsules. Blue capsules will contain 100 mg pregabalin or placebo; green capsules will contain 25 mg pregabalin or pregabalin placebo. These medications have not been used together and it is likely that doses will need to be held or reduced due to side effects. The most likely side effect from lofexidine is hypotension and/or bradycardia. The most likely side effect from pregabalin is sedation. Thus, in the event of hypotension, the next scheduled dose of lofexidine can be reduced or withheld. A similar adjustment can be made for excessive sedation (POSS score of 3 or 4; difficult to arouse, slurred speech, etc.) For the PENN site, medication counts will be done by the Investigational Drug Service (IDS) pharmacy for each subject. For sites outside PENN, medication counts will be done by the site or site pharmacy.

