7.1.5 Detoxification with Lofexidine. A third detoxification approach emerged with the approval of LFX, a selective alpha 2 adrenergic agonist. Unlike clonidine, it has reduced potency at the A subtype of the alpha 2 receptor and is associated with less bradycardia and hypotension (Yu et al, 2008; Gowing et al, 2016). Though its effects are similar to clonidine, its better safety profile is an advantage, especially in outpatient settings where hypotension can be a problem (Kahn et al, 1997; Lin et al, 1997; Carnwarth & Hardman, 1998). Like clonidine, it does not target the withdrawal- related subjective effects, thus potentiating a greater likelihood for dropout. An inpatient study randomized OUD inpatients to detoxification using lofexidine or diazepam. Twenty-seven percent (15/55) of the diazepam patients completed 10 days of treatment, vs 46.4% (26/56) of the lofexidine patients, thus more effective than diazepam although with much room for improvement (Guo et al, 2018). In a pivotal study leading to FDA approval, lofexidine showed a small reduction in subjective effects compared to placebo (a 2-point difference on the SOWS-Gossop scale) with significantly greater rates of detoxification completion (41% vs 28%; Fishman et al 2018). Again, showing the need for improvement, particularly for patients transitioning to antagonist therapy.

7.1.6 Detoxification with Pregabalin and Lofexidine. Here we propose to see if PGB can be safely combined with LFX to better reduce the subjective effects of opioid withdrawal and increase the proportion that transition to antagonist treatment. Such an approach could lower the detoxification hurdle for patients who are interested in antagonist treatment or in settings where agonist treatment is unavailable or difficult to access, and reduce overdose risk for those who make the transition. This study, will attempt to identify a PGB/LFX combination that reduces withdrawal- related subjective effects without generating more SAE's than LFX, as a precursor to a larger trial. The combination of PGB and LFX may result in increased drowsiness, lightheadedness and trouble concentrating.

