This study is a phase II, double-blind placebo-controlled, study to examine whether: 1) PGB can be combined with LFX and reduce opioid withdrawal-related subjective effects; and, 2) if safe and effective, can the combination increase the proportion of OUD subjects who transition to XR-NTX. To investigate these objectives, preliminary data on the safety and tolerability of PGB/LFX dose sequencing, and the reduction of opioid withdrawal-related subjective effects, will be obtained in the current trial. We will use a two-arm comparison; PGB/LFX versus LFX/PGB-PLA. If the current trial shows that a PGB/LFX combination is likely to be safe effective, and reduces opioid withdrawal related subjective effects, we will conduct a second trial in which we will test the PGB/LFX combination in a larger sample, under well- powered conditions, to evaluate the results of the current trial in relation to the efficacy of the combination to reduce opioid withdrawal-related subjective effects and possibly increase the proportion of patients who complete detoxification and transition to XR-NTX treatment. The first 2-year component will utilize three sites with inpatient units. Each site will recruit around 30 randomized subjects for a total sample size of 90 using DSM-5 criteria to establish

OUD with physiologic features diagnosis.

This trial has 4 distinct phases (see 4.0: Figure 1 schematic): 1) Screening (up to 30 days before inpatient admission and randomization). Patients who were never randomized and who come back after 30 days must be reevaluated and assigned a new screening number; 2) Inpatient Detox (1 – 7) days for medication induction and other assessments, 3) Inpatient administration of XR-NTX (Day 8); and, 4) Outpatient Follow-Up (Day 10 and Day 15). Dosing for lofexidine and pregabalin will begin at 12:00 on day 1 and be tapered starting at day five. This plan will permit dose adjustments for adverse effects, such as BP <90 mmHg systolic or <60 mmHg diastolic, a clinically significant drop in standing vs sitting blood pressure, bradycardia <50 bpm, or excessive sedation. Subjects that need a procedure repeated can continue inpatient treatment through day 9. The Study Schema is seen above in 4.0, Figure 1: Overview of Study Schematics Pregabalin (LYRICA®) plus Lofexidine (LUCEMYRATM)". Study assessments are seen in 5.0 Table 1.

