7.3.2 DOSING SCHEDULES

Table 2: LFX Dosing: all tablets are 0.18 mg

	Time	Day 1	Day 2	Day 3	Day 4	Day 5	Day 6	Day 7
All	0800	0.00	0.54	0.54	0.54	0.54	0.36	0.18
Groups								
	1200	0.54	0.54	0.54	0.54	0.36	0.18	0.18
	1600	0.54	0.54	0.54	0.54	0.36	0.18	0.18
	2000	0.54	0.54	0.54	0.54	0.36	0.18	0.18
	Total	1.62	2.16	2.16	2.16	1.62	0.90	0.72

Table 3: PGB and PGB-PLA Dosing (in mg)

	Time	Day 1	Day 2	Day 3	Day 4	Day 5	Day 6	Day 7
Group 1	0800	0	200	200	200	100	50	25
(PGB)	1200	100	100	100	100	75	25	25
	1600	100	100	100	100	75	25	25
	2000	200	200	200	200	150	100	25
	Total	400	600	600	600	400	200	100
Group 2	0800	0	PLAC	PLAC	PLAC	PLAC	PLAC	PLAC
(PGB-PLA)	1200	PLAC						
	1600	PLAC						
	2000	PLAC						
	Total	0	0	0	0	0	0	0

7.3.3 Dosing Guidelines:

As stated below investigators may choose to stop or reduce the dose of either Study Medication although BP and pulse changes are more likely to be due to lofexidine and sedation due to pregabalin.

- Patients can be started and continued on Study Medication if the pulse is 50 or above. Medication should be held if the pulse is <50.
- Patients can be started on Study Medications on Day 1 if COWS >/=6 and SOWS_>/= 4
- A study physician is required to hold the dose of Study Medication if the systolic BP is < 90 and/or the diastolic is <60. Investigators should hold both lofexidine and pregabalin until the next dosing time when they can be restarted if the vitals return to 90/60 or above.
- Hypotension is a potential side effect of lofexidine; sedation, dizziness, or light-headedness are
 potential side effect of pregabalin. A drop of 20 mm or more systolic and/or 10 mm or more diastolic;
 or significant lightheadedness or dizziness, are grounds for holding or reducing a dose of the
 medication that is the most likely cause. Investigators should use their judgement on which Study
 Medication to hold or reduce and by how much.
- **7.3.3.1** The following procedures will minimize risks associated with transient vs. persistent BP changes:
 - If the BP reading shows a pre-medication sitting and/or standing drop (orthostatic change) of more than 20mm systolic, and/or more than 10 mm diastolic, wait 2-3 minutes and repeat the sitting and standing BP.

- If the repeat readings are within the acceptable range as defined by the protocol, dosing can be continued as planned.

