- **7.4.4 ECG and Vital Signs.** ECGs will be reviewed each day before administration of the first dose of study medication. Medication will be withheld if there is clinically significant QTc prolongation. Vital signs will be checked sitting and standing pre-dose and 1-2 hours post dose. Study medication will be withheld if the seated systolic BP is below 90 systolic or below 60 diastolic, and/or if the pulse is <50. A study physician will be contacted for dosing instructions if the seated systolic BP is >20 mm, or >10 mm diastolic below the last reading. Study medications may also be withheld or reduced if there is excessive sedation or other clinically significant AE's that may be caused by study medication. First degree AV block is common and does not indicate a serious problem. Study medication should be stopped and the study cardiologist contacted if there is 2nd degree heart block.

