Subjects are admitted to the inpatient unit, randomized to one of the two study medication conditions, and will need to demonstrate withdrawal before starting study medications by having a COWS >/= 6 and a SOWS >/= 4. LFX and PGB dosing will begin at 12:00 on day 1 and a study drug taper will be done from days 5-7. Dose times follow the schedule outlined above and adjustments will be made based on BP changes and/or other AEs. Administration of LFX will be withheld or reduced in cases of dizziness or lightheadedness, clinically significant hypotension and/or the BP changes described above. We will explain to participants the importance for adequate oral hydration during the consenting process and throughout the detox. Similar procedures will be applied to PGB in cases of excessive sedation, dizziness, peripheral edema, or other problematic side effects that appear related that medication.

Dosing schedules are in Tables 2 and 3. Assessments for Day 1 through 7 include:

- 1) ECG is obtained before the 12:00 dose of study medications on Day 1 and before the 08:00 dose of study medications on Day 2-7
- 2) VAS is given before the first dose of study medication at 12:00 on Day 1 and before the 16:00 dose on Day 1. On Day 2-7, the VAS is given before the first dose of study medications at 08:00 and before the 16:00 dose of study medications
- 3) ISI given before the 12:00 dose of study medications on Day 1, and before the 08:00 dose of study medications on Days 2-7
- 4) COWS is given around 12:00 on Day 1 before the first dose of study medication; and around16:00 before the next dose of study medication. If subject is admitted without the requisite withdrawal (COWS >/= 6 and SOWS >/= 4), subsequent COWS and SOWS can be administered before the first dose of study medication until dosing criteria is met.
- 5) SOWS-G is given around 12:00 on Day 1 before the first dose of study medication; and around 16:00 before the next dose of study medication
- 6) POSS is given prior to all doses (08:00, 12:00, 16:00 and 20:00) of study medication
- 7) Sitting and standing blood pressure and pulse are taken prior to each dose of study medication and 1 to 2 hours after dosing, (can use manual blood pressure check if considered necessary)
- 8) Weight taken 1x at screen and Day 15 and recorded on the physical form
- 9) Adverse events/SAEs recorded daily
- 10) Concomitant medication records reviewed and recorded each day
- 11) C-SSRS is given at the end of each study day

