13.0 STATISTICAL PLAN

13.1 DATA ANALYSES

[name], the CSA Statistician, and his staff will perform data analyses. Prior to analyses, standard data screening/cleaning procedures will be applied. These procedures will screen the data for data-entry errors, check for outliers, assess the extent and pattern of missing data, and check that appropriate assumptions of normality are met whenever necessary.

13.2 **SAMPLE SIZE DETERMINATION**

Power Analyses: The primary goal of this study is to determine if the PBG/LFX combination versus LFX/PGB-PLA is safe and effective in OUD individuals, and shows a reduction in opioid–related withdrawal effects greater than lofexidine alone. To assist in this determination, we provide power for the primary comparison of longitudinal subjective withdrawal measures, comparing the groups on rate of decrease across days, using a linear group by time effect for the mixed effects models described above. We have one primary outcome, so use an alpha level of 0.05, and we use two- sided tests. 90 subjects, approximately 30 from each of three sites (MMTC and PENN might have more than 30), who will be randomized into two groups, with 30 assigned to LFX/PGB-PLA, and 60 to LFX plus a starting daily dose of 400 mg of PGB and increasing to 600mg PGB on day 2. Assuming an overall dropout rate of 40%, and within-subjects' correlations of 0.5, the methods of Hedeker et al (Hedeker, Gibbons and Waternaux, 1999) show that this provides 80% power for a group by linear time interaction effect of Cohen's d=0.44 standard deviations between the two groups.

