13.8 VITAL SIGNS

Vital sign data (HR and BP) will be presented as summary statistics of maximum (max) absolute values, max change from baseline, and time to max value during the 1-hour period after each dose of study medication. Data will be compared between groups and within groups by study day by Wilcoxon rank sum statistic. Effects will be considered statistically significant at a two-sided p < 0.05.

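### Section 13.8 analyses vital signs in the hour after each dose, when no reading is scheduled, and names maxima but no minimum or sit-to-stand drop, so it is not specified to show whether pregabalin worsens low blood pressure or slow pulse.

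*Combined protocol and SAP*

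**What the plan says.** Section 13.8 summarises heart rate and blood pressure as "maximum (max) absolute values, max change from baseline, and time to max value during the 1-hour period after each dose". These are compared between and within groups, by study day, with the Wilcoxon rank-sum test at a two-sided 0.05 level.

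The measurement schedule is set elsewhere:

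- Section 7.4.4: "Vital signs will be checked sitting and standing pre-dose and 1-2 hours post dose".
- Section 9.1.2, item 7: "Sitting and standing blood pressure and pulse are taken prior to each dose of study medication and 1 to 2 hours after dosing".
- Section 10.11, item 3, gives the same 1 to 2 hour post-dose timing.
- The Table 1 footnote gives one pre-dose and one post-dose set per dose, with no minutes.

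The protocol also says which vital-sign changes it expects. The note in Section 3.0 states: "The most likely side effect from lofexidine is hypotension and/or bradycardia". Section 7.1.6 gives as reasons for dose adjustment "BP <90 mmHg systolic or <60 mmHg diastolic, a clinically significant drop in standing vs sitting blood pressure, bradycardia <50 bpm". Sections 7.3.3, 7.4.4 and 19.2 set the dosing limits around 90 systolic, 60 diastolic and, in the first two, a pulse of 50; all three also refer to blood pressure drops of about 20/10 mmHg.

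**The concern.** Section 13.2 puts safety within the trial's main aim: "The primary goal of this study is to determine if the PBG/LFX combination versus LFX/PGB-PLA is safe and effective in OUD individuals". Lofexidine is given in both arms, so the haemodynamic question between arms is whether adding pregabalin worsens hypotension, orthostatic drop or bradycardia. Section 7.1.6 points the same way, though weakly: "The combination of PGB and LFX may result in increased drowsiness, lightheadedness and trouble concentrating".

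Section 13.8 is the only analysis in the plan that compares blood pressure or pulse between arms. Sections 13.4 and 13.5 cover suicidality, sedation, creatine kinase, edema, achiness, anxiety and insomnia. If 13.8 is run as written, it is nearly empty or uses only off-schedule readings. It also leaves open, until the data are in hand, whether a fall counts as a change, which posture is used and which baseline applies. This result would inform the decision in Section 7.1.6 on whether to run a larger trial.

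**Working it through.** The plan gives no power or event figure for vital signs, so there is none to reproduce. The first two steps use only the documents; steps 3 to 5 add stated assumptions.

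**1. Window.** For a dose at time *d*, the analysis window runs from *d* to *d* + 1 h and the scheduled reading falls between *d* + 1 h and *d* + 2 h. At 08:00, 12:00, 16:00 and 20:00 the overlap is 0 hours; only the 60-minute point is shared. Tables 2 and 3 give 3 doses on Day 1 and 4 on each of Days 2 to 7: 3 + 4 × 6 = 27 post-dose time points per patient (28 if the 8X entry for Day 1 in Table 1 is taken literally). None is scheduled before 60 minutes. The retest within an hour in Section 7.3.3.1 applies only after out-of-range readings.

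Actual times will scatter. Assuming a normal distribution with SD 15 minutes:

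- target 90 minutes: Φ((60 − 90)/15) = 0.023; × 27 = 0.6 readings inside the window;
- target 75 minutes: Φ((60 − 75)/15) = 0.159; × 27 = 4.3 readings.

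All of these would be off schedule.

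**2. Time to maximum.** With one post-dose time point per dose, the time of that reading is the only possible answer. It says nothing about when the peak occurred.

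**3. Direction.** Take an assumed baseline of 125 mmHg and two days of post-dose systolic readings.

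| Readings | Maximum | Most positive change | Largest unsigned change | Minimum | Largest fall |
|---|---|---|---|---|---|
| 125, 110, 84, 120 | 125 | 0 | 41 | 84 | 41 |
| 125, 122, 118, 120 | 125 | 0 | 7 | 118 | 7 |

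The maximum and the most positive change cannot tell the days apart. The unsigned change can.

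**4. Size of the effect.** Simulation with 60 against 30 patients, one day, four post-dose seated systolic readings, rank-sum test at 0.05, 1,500 runs, no dropout. Assumed: mean 118, between-patient SD 12, within-patient SD 8, an 8 mmHg post-dose fall in both arms, and a separate baseline reading. The window problem is ignored here, to isolate the choice of measure. Power:

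| Extra fall in pregabalin arm | Maximum | Most positive change | Unsigned change | Minimum | Largest fall |
|---|---|---|---|---|---|
| 15 mmHg, one random dose of four | 8% | 8% | 91% | 70% | 92% |
| 10 mmHg, one random dose of four | 7% | 9% | 44% | 28% | 46% |
| 5 mmHg, every dose | 39% | 59% | 46% | 38% | 58% |
| None | 5% | 5% | 5% | 5% | 5% |

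A second model, with between-patient SD 10, within-patient SD 8 and 25 mmHg dips on 5% of control readings, gives the same picture. With dips on 15%, 25% and 35% of pregabalin readings, the maximum is significant in about 6%, 9% and 14% of trials and the minimum in about 37%, 85% and 99%.

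**5. Test.** Within a group the same patients are compared with themselves, but the rank-sum test treats the samples as independent. With n = 60, a true shift of 0.4 SD and assumed correlations of 0.3, 0.5 and 0.7 (4,000 runs), rank-sum power is 58%, 61% and 61% against 71%, 85% and 97% for the signed-rank test. The rank-sum false-positive rate falls from 2.4% to about 0%. The error is conservative but loses sensitivity.

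If one between-arm test is run per vital sign (3), measure (3) and day (7), that is 3 × 3 × 7 = 63 tests, with 63 × 0.05 ≈ 3 false positives expected if there is no effect.

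**The case against.** The strongest reply is that the largest change from baseline can be read as the largest in either direction. On that reading it has 91% power in the first scenario, almost the same as the largest fall, and the defect is a missing word. This stands as far as it goes: 13.8 is under-specified, not shown to be blind to falls. But leaving the sign open until after the data are seen is itself the problem, and the reply does nothing for the window.

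A fall after one random dose is also the case least favourable to the maximum. Both drugs are given several times a day and lofexidine accumulates (Section 7.4), so a sustained shift is plausible. An extra 8 mmHg after every dose gives about 73% power for both maximum and minimum. This stands: the loss from using maxima concerns intermittent falls.

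The protocol attributes blood pressure and pulse changes mainly to lofexidine, which both arms receive, and Section 11.9 lists increases in vital signs as a withdrawal sign, so maxima have some use. That argues for adding minima, not for omitting them. Whether pregabalin adds to lofexidine's effect is still the between-arm question.

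Finally, patients are protected in real time. Section 7.3.3 says: "A study physician is required to hold the dose of Study Medication if the systolic BP is" below 90 and/or the diastolic is below 60. The data and safety monitoring board sees unblinded adverse events, and the primary endpoint is withdrawal severity. All true, and no patient protection or primary result fails. But Section 15.1 counts an abnormal result as an adverse event only under certain conditions, Section 13.7 describes recording and not comparison, and Section 10.12 only lists vital signs as considered. None of these is a pre-specified comparison of blood pressure or pulse.

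**Conclusion.** The concern holds and should be corrected before unblinding. From the documents alone, the analysis window and the scheduled readings share only the 60-minute point, time to maximum cannot be estimated, and no minimum, sit-to-stand drop or threshold proportion is named. Posture, baseline, the sign of the change and the way a day's doses are combined are also left undefined. The only specified between-arm comparison of blood pressure and pulse therefore cannot be run as written on scheduled data.

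The power figures are illustrations. They depend on assumed means, SDs and fall patterns, ignore dropout and held doses, and show a loss for intermittent falls but not for a uniform shift. The counts of 0.6 and 4.3 readings rest on an assumed 15-minute scatter and assumed target times. The window and time-to-maximum defects need none of these assumptions.

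**What to change.** Rewrite Section 13.8 as follows.

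- Replace the 1-hour window with the scheduled pre-dose and 1 to 2 hour post-dose readings, and delete time to maximum.
- By study day and arm, report the minimum seated systolic pressure, diastolic pressure and pulse; the largest decrease from a stated baseline; the largest sit-to-stand drop; and the proportion of patients with any reading below the protocol's own limits (90 systolic, 60 diastolic, 50 bpm).
- State the posture for each measure and how the doses of a day are combined. Maxima may stay as an additional summary if wanted for withdrawal.
- Use a paired or repeated-measures method within groups.
- State that these are safety summaries without multiplicity control, and that doses held or reduced for low readings affect later values.

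The choice of baseline, and any adjustment for site or sex, is open as long as it is stated. The cost is a wording amendment and a little more analysis. All readings are already collected, and no dosing or hold rule changes.

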3.0 PROTOCOL SUMMARY

Title	Combining Pregabalin (LYRICA®) with Lofexidine (LUCEMYRA™): Can it Increase the Success of Transition to Naltrexone?						
Short Title	Pregabalin and Lofexidine for opioid withdrawal						
Protocol Version	7.0						
Phase	Phase 2						
Methodology	Double-blind placebo-controlled parallel group clinical trial						
Study Duration	24 months						
Study Centers (3)	 University of Pennsylvania Center for Studies of Addiction in Philadelphia Pennsylvania Columbia University in New York City, New York Mountain Manor in Baltimore, Maryland 						
Objective (Primary)	To investigate whether pregabalin-Lyrica® (PGB) combined with Lofexidine-Lucemyra® (LFX) can reduce opioid withdrawal-related subjective effects						
Objective (Secondary)	To investigate, if the PGB/LFX combination can increase the proportion of patients with an opioid use disorder (OUD) who complete detoxification and transition to antagonist treatment with extended- release injectable naltrexone VIVITROL® (XR-NTX)						
Number of Subjects	90 subjects. 60 randomized to PGB/LFX; 30 to PGB-PLA/LFX						
Inclusion Criteria	 Male and/or female subjects ≥ 18 years of age Meet DSM-5 criteria for an Opioid Use Disorder with physiologic features. Have 2 or more of the 11 DSM 5 criteria for opioid disorder including tolerance and withdrawal features in the last 12 months Interested in opioid antagonist treatment Have used opioids in 20 of the past 30 days Have a stable address in the local area; not planning to move; have documents for ID check Absence of medical or psychiatric conditions that are likely to interfere with study participation Have a 12 lead ECG demonstrating a QTc ≤450 msec and a QRS interval ≤120 msec. The site PI has the final determination for inclusion into the study for ECGs unless there is a question of QT prolongation or other factors (QTc/Fri uses the Fridericia formula (QTc = QT/RR(1/3)). If consultation is needed, the PENN cardiologists and the medical monitor should be contacted. If female, have a negative pregnancy test, and uses adequate contraception if of childbearing potential 						

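### Section 13.8 applies the Wilcoxon rank-sum test, an independent-samples test, to within-group vital-sign comparisons on the same patients, so those p-values are not valid

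*Combined protocol and SAP*

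**What the plan says.** Section 13.8 defines the vital-sign variables as "summary statistics of maximum (max) absolute values, max change from baseline, and time to max value during the 1-hour period after each dose". It then names one test for two kinds of comparison: "Data will be compared between groups and within groups by study day by Wilcoxon rank sum statistic". The criterion is "Effects will be considered statistically significant at a two-sided p < 0.05".

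The readings are repeated measures. Section 9.1.2 says: "Sitting and standing blood pressure and pulse are taken prior to each dose of study medication and 1 to 2 hours after dosing". Tables 2 and 3 give three dosing times on Day 1 and four on Days 2 to 7.

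Section 13.8 names no paired test and no mixed model. It does not say which days are contrasted, what baseline is, or whether a day's readings are reduced to one value per patient. Elsewhere in section 13 the repeated measures (the SOWS total, POSS, the achiness and anxiety items, and the ISI) all get mixed-effects models.

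**The concern.** The rank-sum test takes its null variance from two unrelated samples. In a within-group comparison, whether day against day or day against baseline, the same patients supply both sides and their values are correlated. The nominal 5% level then no longer holds.

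The protocol summary names hypotension and bradycardia as the most likely lofexidine side effects and says the two drugs have not been used together. Both arms receive the same lofexidine schedule, so the between-group test shows only what pregabalin adds. The within-group comparison is the only planned vital-sign test of the total change under the combination. A non-significant result could be read as reassurance before the larger trial foreseen in section 7.1.6.

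**Working it through.** **The plan's own figure.** Section 13.8 states no power. The only power figure is in 13.2, for the SOWS: "this provides 80% power for a group by linear time interaction effect of Cohen's d=0.44 standard deviations between the two groups". A generalised least squares calculation with compound symmetry 0.5 and 30 versus 60 patients gives 77.5% with 14 occasions and dropout rising linearly to 40%, 79.6% with 15 occasions, and 80.2% with 10 occasions and no dropout. Section 13.2 does not state the number of occasions, so this is no ground for calling 80% wrong, and it does not bear on 13.8.

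**Inputs.**
- Group sizes, section 3.0: "90 subjects. 60 randomized to PGB/LFX; 30 to PGB-PLA/LFX".
- Section 13.2: "Assuming an overall dropout rate of 40%, and within-subjects' correlations of 0.5". Hence 60 × 0.6 = 36 and 30 × 0.6 = 18 patients at the end.
- The correlation of 0.5 is stated for the withdrawal score. Its use for vital signs is an assumption, so 0.3 to 0.7 is shown.
- The documents give no SD and no relevant fall for heart rate or blood pressure. Shifts are in SD units; 0.4 SD is an assumed modest shift.

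**Case A: one value per patient per day.** With correlation ρ, the rank-sum z statistic has standard deviation √(1−ρ) under the null instead of 1.

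True type I error = 2 × [1 − Φ(1.96/√(1−ρ))]. At ρ = 0.5: 1.96/0.707 = 2.77, giving 0.0056. At 0.3 it is 0.019 and at 0.7 it is 0.0003. Simulation gives about 0.02, 0.007-0.008 and 0.001. The signed-rank test stays at about 0.05.

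For a shift of d SD, let c = d × √(n/(2(1−ρ))).
- Paired power ≈ Φ(c − 1.96).
- Rank-sum power ≈ Φ((c√(1−ρ) − 1.96)/√(1−ρ)).

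At d = 0.4, n = 36, ρ = 0.5: c = 0.4 × 6 = 2.40. Paired power is Φ(0.44) = 67%. Rank-sum power is Φ((1.697 − 1.96)/0.707) = Φ(−0.37) = 36%. The formula is for means and runs slightly high for rank tests.

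| ρ | Rank-sum, formula | Paired, formula | Rank-sum, simulated | Signed-rank, simulated |
|---|---|---|---|---|
| 0.3 | 38% | 53% | about 34% | about 47-49% |
| 0.5 | 36% | 67% | about 33-34% | about 64% |
| 0.7 | 32% | 87% | about 30% | about 84-85% |

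With all 60 patients and ρ = 0.5, the simulated figures are 60% and 85%.

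For a shift set at 80% paired power by the normal formula, with ρ = 0.5, simulated power is 44-48% for the rank-sum and 73-77% for the signed-rank. The rank-sum has 61-64% at ρ = 0.3 and 20-22% at ρ = 0.7.

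For a 1 SD shift, the rank-sum detects at least 83% in every case tried (n = 18 to 60, ρ = 0.3 to 0.7). At ρ = 0.5 it is 87% for n = 18 and 99% for n = 30.

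**Case B: four readings per day pooled as independent.** Let w be the correlation within a day and b between days. The true variance of the within-group difference is the assumed variance times V = 1 + 3w − 4b, and type I error is 2 × [1 − Φ(1.96/√V)].
- w = 0.5, b = 0.5: V = 0.5, error 0.006 (simulated 0.0065, n = 60).
- w = 0.7, b = 0.5: V = 1.1, error 0.062 (simulated 0.076).
- w = 0.7, b = 0.3: V = 1.9, error 0.155 (simulated 0.15).

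Between groups, V = 1 + 3w. For w = 0.3, 0.5 and 0.7, V is 1.9, 2.5 and 3.1, giving 0.155, 0.215 and 0.266 (simulated 0.14-0.27).

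**The case against.** A reader might infer that real falls in blood pressure or heart rate are generally likely to be missed. The documents do not support that. They give no SD and no relevant fall, 0.4 SD is an assumption, and 1 SD shifts are still usually found. Whether falls are captured at all also depends on what maximum change means in 13.8, which is a separate question.

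A reader might also infer that the error always runs toward false reassurance. That requires one value per patient per day, which 13.8 does not state. Under pooling it can produce false positives.

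Nor does the plan assume a correlation of 0.5 for vital signs; that figure belongs to the withdrawal score. The end-of-study sizes of 36 and 18 understate the patients present on earlier days.

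Other limits stand. A within-arm change mixes lofexidine, the taper and resolving withdrawal, so it cannot isolate pregabalin. Individual falls are handled by the hold rules in 7.3.3 and 7.4.4, the criteria in 19.2 and the DSMB review of adverse events, none of which uses this test. The wording may be partly loose: it does not name the within-group contrast, and change from baseline is already a paired difference, to which a two-sample test against zero cannot be applied.

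These points limit the consequence. They do not make an independent-samples test valid for repeated readings, and no other section supplies a paired analysis for vital signs.

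**Conclusion.** The within-group test in 13.8 is wrong as written and should be corrected. The mismatch follows from the text alone; only its size and direction rest on assumptions.

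With one value per patient per day and correlation 0.3 to 0.7, the test is too conservative, and for modest shifts it loses between roughly a quarter and two thirds of the signed-rank test's power (34% against 47%; 30% against 85%). With dose readings pooled as independent, the level can be too low or too high depending on correlations the documents do not give, and the between-group comparison is then affected too.

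The effect is confined to group-level within-group inference. It does not touch the primary outcome, the randomised between-group vital-sign comparison when each patient contributes one value, or bedside safety management.

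**What to change.** Amend 13.8 to state:
- one prespecified value per patient per day for each vital sign, and how it is derived from the dose readings;
- the baseline and the day contrasts to be tested;
- the rank-sum test for between-group comparisons only;
- for within-group comparisons, the Wilcoxon signed-rank test on each patient's paired difference from the stated baseline, or a linear mixed model with day as a factor, in line with the rest of section 13.

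The cost is one or two sentences. No new data, visits or patients are needed.
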